6.6.5 Schedule of Events

The schedule of activities specific to this clinical investigation are described in the preceding sections and are summarized in **Table 4**.

Table 4. Schedule of Clinical Investigation Activities

Activity	Enrollment / Baseline	Procedure (~14-days of consent)	Pre-Discharge (>12 hrs and <72 hrs post-proc.)	7-Day Phone Call (± 2 days)	3-Month In-Person (91±14 days)	6-Month Phone Call ⁶ (181±30 days)	12-Month Phone Call ⁶ (365±30 days)	15-Month In-Person (450±30 days)
Informed Consent Process	X							
Demographics	X							
Medical History	X							
Cardiovascular History	X							
AAD & Anticoagulant Medications	X		X	X	X	X	X	X
Physical Examination	X		X					
Neurological Assessment & NIHSS	X		X ⁵					
Diffusion-weighted MRI - Brain	(X)		(X)					
NYHA	X							
CHA ₂ DS ₂ -VASc score	X							
12-Lead ECG	X ⁷		X		X			X
AFEQT & EQ-5D-5L Questionnaires	X				X	X	X	X
24-Hour Holter	X ⁷				X	X	X	X
Urine Pregnancy Test		(X)						
Confirm absence of thrombus		X ¹						
Ablation procedure		X						
TTE or ICE		X ²	(X) ²					
Trans-Telephonic Monitoring (TTM)					X ³	X ³	X ³	X ³
CT or MRI of pulmonary veins				(X)	(X)	(X)	(X)	(X)
Adverse Event Assessment	X	X	X	X	X	X	X	X
Document Deviations	X	X	X	X	X	X	X	X
Document Cardiovascular Healthcare Utilization	X ⁴		X ⁴	X ⁴	X ⁴	X ⁴	X ⁴	X ⁴
Withdrawal	(X)	(X)	(X)	(X)	(X)	(X)	(X)	(X)
Death	(X)	(X)	(X)	(X)	(X)	(X)	(X)	(X)

(X) If applicable

1. Thrombus assessment must be performed the day prior to or on the day of the procedure. If a thrombus is discovered, the procedure should be postponed and the subject placed on anticoagulation until the thrombus is resolved as confirmed by imaging.
2. TTE or ICE imaging must be performed prior to the conclusion of the procedure to exclude pericardial effusion.

3. TTM are collected monthly and whenever the subject is experiencing a symptomatic episode starting at 3-months post-procedure to 15-months.
4. At each scheduled visit, the subject will be interviewed to determine if they have had any cardiac-related hospitalizations (inpatient or outpatient), emergency room visits, and/or urgent care visits since the last scheduled study visit and a healthcare utilization form completed. Additionally, healthcare utilization in the year previous to enrollment in this trial will be assessed.
5. The neurological exam and NIHSS must be performed >12 hours, but no later than 36 hours after the procedure.
6. The 6 and 12-month visits are phone calls to the subject. However, these visits may be conducted in-person as well.
7. Either a 24-hr Holter or 2 ECGs obtained ≥ 7 days apart may be used to demonstrate continuous AF at Baseline.

6.7 Core Laboratory

A core lab will be used for the collection, interpretation, and collation of data collected from the following sources:

- TTM
- 24-hour Holter monitoring
- 12-lead ECGs

The core lab will provide independent review of this data by appropriately trained personnel using standardized procedures to interpret TTM, 24-hour Holter, and 12-lead ECG tracings for adjudication of atrial arrhythmias. Findings will be communicated to the investigator and to Abbott. The core lab's adjudication findings will be used for analysis.

7 ADVERSE EVENTS

To comply with worldwide standards and guidelines on clinical investigation adverse event reporting, the Sponsor has adopted uniform and worldwide applicable standard definitions and reporting timelines to be used and adhered to by the investigators.

7.1 Definitions

7.1.1 Adverse Event

An adverse event (AE) is any untoward medical occurrence, unintended disease or injury, or untoward clinical signs (including abnormal laboratory findings) in subjects, users or other persons, whether or not related to the medical device under investigation.

7.1.2 Serious Adverse Event

If the AE meets any of the criteria below, it is regarded as a serious adverse event (SAE).

- a) Led to a death,
- b) Led to a serious deterioration in health of the subject, that either resulted in
 1. a life-threatening illness or injury, or
 2. a permanent impairment of a body structure or a body function, or
 3. in-patient hospitalization or prolongation of existing hospitalization, or

4. medical or surgical intervention to prevent life threatening illness or injury or permanent impairment to a body structure or a body function.
 5. chronic disease
- c) Led to fetal distress, fetal death or a congenital abnormality or birth defect.

NOTE: A planned hospitalization for a pre-existing condition, or a procedure required by the CIP, without a serious deterioration in health, is not considered to be an SAE.

7.1.3 Device Deficiency/Device Malfunction

Device deficiency is defined as an inadequacy of a medical device related to its identity, quality, durability, reliability, safety or performance, such as malfunction, misuse or use error and inadequate labeling. This includes the failure of the device to meet its performance specifications or otherwise perform as intended. Note: Performance specifications include all claims made in the labeling of the device.

A device malfunction is the failure of a device to meet its performance specifications or otherwise perform as intended, when used in accordance with the instructions for use or CIP.

7.2 Device Relationship

Determination of whether there is a reasonable possibility that an investigational product or device under investigation caused or contributed to an AE is to be **determined by the Investigator** and recorded on the appropriate CRF form. Determination should be based on assessment of temporal relationships, evidence of alternative etiology, medical/biologic plausibility, and patient condition (pre-existing condition).

7.2.1 Adverse Device Effect (ADE)

The following definition will be used to categorize non-serious procedure or device-related AEs:

- An adverse event related to the use of an investigational medical device.
- This definition includes adverse events resulting from insufficient or inadequate instructions for use, deployment, implantation, installation, or operation, or any malfunction of the investigational medical device.
- This definition includes any event resulting from the use error or from intentional misuse of the investigational medical device.

7.2.2 Serious Adverse Device Effect (SADE)

The following definition will be used to categorize serious procedure or device-related AEs:

- Adverse device effect that has resulted in any of the consequences characteristic of a serious adverse event.
- This definition includes events related to the investigational medical device or the comparator.

7.2.3 Unanticipated Device Effect (UADE) – United States only

Unanticipated serious adverse device effect (UADE) refers to any serious adverse effect on health or safety or any life-threatening problem or death caused by, or associated with, a device, if that effect, problem, or death was not previously identified in nature, severity, or degree of incidence in the investigational plan or application (including a supplementary plan or application), or any other unanticipated serious problem associated with a device that relates to the rights, safety, or welfare of subjects.

7.3 Adverse Event and Device Deficiency/Device Malfunction Reporting

7.3.1 Adverse Event Reporting

Safety surveillance and reporting starts as soon as the patient is enrolled in the clinical investigation. Adverse event data, including deaths, will be collected starting at the time of enrollment (after consent and eligibility criteria are met) and throughout the 15-month follow-up period and will be reported to the Sponsor on the Adverse Event CRF. Safety surveillance and reporting will continue until the last follow-up visit has been performed, the subject is deceased, the subject concludes participation in the clinical investigation or the subject withdraws from the clinical investigation.

For the purposes of this clinical investigation, the following adverse events will be reported:

- Adverse events that are assessed by the investigator as being related to either the ablation catheter or the ablation procedure will be reported in the database, preferably within 7-days of the site learning of the event
- Serious adverse events, regardless of relatedness to the procedure and/or the ablation catheter will be reported as described in **Section 7.3.2**.

Recurrence of AF, AFL, or AT are not considered reportable adverse events unless they occur in severity, frequency, or other manner that is significantly worse than the subject’s baseline condition. Recurrence of AF, AFL, or AT will affect the primary effectiveness endpoint and should be reported on the Follow-Up Visit CRF.

Additionally, urinary tract infections (UTIs) that occur after a procedure and do not require a Foley catheter will not be considered adverse events. UTIs that require a Foley catheter will be reported as AEs if related to the procedure or meet serious criteria.

Unchanged, chronic, non-worsening or pre-existing conditions are not AEs and should not be reported.

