3.2 Measures Taken to Avoid and Minimize Bias

Multiple measures will be taken to avoid and minimize bias in this clinical investigation. First, PERSIST-END is a prospective clinical investigation in which the outcome is unknown at the time of enrollment and

all subjects must meet the defined eligibility criteria to minimize selection bias. Next, guidance will be provided to sites regarding data collection for questionnaires and the post-procedure follow-up phone calls to be performed at 7-days, 6-months, and 12-months post-procedure. Additionally, case report forms for data collection will be provided to sites, which will minimize inter-observer variability.

Evaluation of primary endpoint data will be performed by an independent core laboratory and Clinical Events Committee (CEC). Collected electrocardiogram (ECG), trans-telephonic monitoring (TTM) data, and 24-hour Holter data from sites will be evaluated by a physician at a core laboratory to determine AF recurrence for subjects. Adverse events will be adjudicated by a CEC made up of physicians who are not investigators in the trial. Although the investigators at each site will perform their own adjudication regarding outcome data, only the core lab and the CEC's adjudication of the collected data will be used for analysis in order to minimize bias.

Protocols are also in place to minimize lost to follow-up subjects and for handling missing data. Sensitivity analyses will be performed demonstrating the impact missing data may have on the trial.

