10.7.2 Clinical Events Committee (CEC)

The Clinical Events Committee is an independent adjudication body comprised of qualified physicians who are not participants in the clinical investigation. The CEC will review and adjudicate pre-specified events reported by investigators or identified by Safety personnel for the clinical investigation as defined in the CEC charter and according to definitions provided in this CIP. The CEC's adjudication of the reported data will be used for analysis.

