APPENDIX III. DEFINITIONS

The following definitions will be used by the CEC to determine whether the events listed below constitute a device or procedure related serious adverse event included in the primary endpoint. Most of the definitions have been adapted from the 2017 HRS/EHRA/ECAS/APHRS/SOLAECE Expert Consensus on AF Ablation.⁴

Primary Safety Event	Description
Atrioesophageal fistula	A connection between the atrium and the lumen of the esophagus. Evidence supporting this diagnosis includes documentation of esophageal erosion combined with evidence of a fistulous connection to the atrium, such as air emboli, an embolic event, or direct observation at the time of surgical repair. A CT scan or MRI scan is the most common method of documentation of an atrioesophageal fistula.
Bleeding	Bleeding is a major complication of AF ablation if it requires and/or is treated with transfusion or results in a 20% or greater fall in hematocrit.
Cardiac tamponade/perforation	The development of a significant pericardial effusion during or within 30 days of undergoing an AF ablation procedure. A significant pericardial effusion is one that results in hemodynamic compromise, requires elective or urgent pericardiocentesis, or results in a 1-cm or more pericardial effusion as documented by echocardiography. Cardiac tamponade/perforation should also be classified as “early” or “late” depending on whether it is diagnosed during or following initial discharge from the hospital.
Death	Adverse event resulting in the patient’s death.
Heart block (AV block)	New, persistent 2 nd or 3 rd degree AV block not attributable to a vasovagal reaction or medication effect and requiring permanent pacing.
Myocardial infarction	Irreversible necrosis of heart muscle secondary to prolonged ischemia with at least one of the following three criteria: (2) Detection of ECG changes indicative of new ischemia (new ST-T wave changes or new LBBB) that persist for more than 1 hour; (3) Development of new pathological Q waves on an ECG; (4) Imaging evidence of new loss of viable myocardium or new regional wall motion abnormality.
Pericarditis	Pericarditis should be considered a major complication following ablation if it results in an effusion that leads to hemodynamic compromise or requires pericardiocentesis, prolongs hospitalization by more than 48 hours, requires hospitalization, or persists for more than 30 days following the ablation procedure.

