### 3.2 Adverse Events

Safety surveillance and reporting starts as soon as the patient is enrolled in the clinical investigation. Adverse event data, including deaths, will be collected starting at the time of consent and throughout the 15-month follow-up period and will be reported to the Sponsor on the Adverse Event CRF. Safety surveillance and reporting will continue until the last follow-up visit has been performed, the subject is deceased, the subject concludes participation in the clinical investigation or the subject withdraws from the clinical investigation.

For the purposes of this clinical investigation, the following adverse events will be reported:

- Adverse events that are adjudicated by the investigator as being related to either the ablation catheter or the ablation procedure
- Serious adverse events, regardless of relatedness to the procedure and/or the ablation catheter

Recurrence of AF, AFL, or AT are not considered reportable adverse events unless they occur in severity, frequency, or other manner that is significantly worse than the subject's baseline condition. Recurrence of AF, AFL, or AT will affect the primary effectiveness endpoint and should be reported on the Follow-Up Visit CRF.

Additionally, urinary tract infections (UTIs) that occur after a procedure and do not require a Foley catheter will not be considered adverse events. UTIs that require a Foley catheter will be reported as AEs if related to the procedure or meet serious criteria.

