## Statistical Analysis Plan

Unchanged, chronic, non-worsening or pre-existing conditions are not AEs and should not be reported.

All adverse events (AEs), adverse device effects (ADEs), serious adverse events (SAEs), serious adverse device effects (SADEs), and unanticipated adverse device effect (UADEs) will be summarized for all subjects enrolled in this trial in terms of the number of events and the percentage of subjects with events.

CEC adjudicated results will be used for analysis. The investigator adjudicated results will be summarized in the final report.

AEs from the FAS population will be summarized separately for subjects who were consented but did not have an investigational catheter inserted into their vasculature from those subjects who are in the PTE population.

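### A listed safety event that the site judges both non-serious and unrelated carries no reporting duty, although Appendix III gives those two judgments to the CEC

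*Protocol*

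**What the plan says.** Protocol 7.3.1 names what sites report. One class is: "Adverse events that are assessed by the investigator as being related to either the ablation catheter or the ablation procedure will be reported". The other is: "Serious adverse events, regardless of relatedness to the procedure and/or the ablation catheter will be reported as described in" section 7.3.2. SAP 3.2 has the same two classes and words the first as "Adverse events that are adjudicated by the investigator as being related to either the ablation catheter or the ablation procedure". Section 7.2 leaves relatedness to the investigator.

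For the analysis, Appendix III states that its definitions "will be used by the CEC to determine whether the events listed below constitute a device or procedure related serious adverse event" that belongs in the primary endpoint. Section 3.2 says: "Although the investigators at each site will perform their own adjudication regarding outcome data, only the core lab and the" CEC's reading of the data that were collected will be analysed, and gives limiting bias as the reason. Section 10.7.2 describes what the CEC sees: "The CEC will review and adjudicate pre-specified events reported by investigators or identified by Safety personnel", with the scope set by a CEC charter that is not among the documents.

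SAP 3.2 also promises a summary, for all enrolled subjects, whose scope begins "All adverse events (AEs), adverse device effects (ADEs), serious adverse events (SAEs), serious adverse device effects (SADEs" and goes on to unanticipated device effects.

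**The concern.** The primary safety endpoint counts listed events that are serious and related to the device or procedure. Appendix III gives both judgments to an independent committee. Section 7.3.1 uses the site's own view of the same two questions to decide what must be entered. If the site answers no to both, no visible rule obliges anyone to record the event, and the committee can adjudicate only what has been collected.

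The trial has one arm and a fixed safety goal (null hypothesis of a rate of 16.8% or more, section 8.2.1.1). No comparator arm exists in which similar under-reporting could offset the loss. An unreported endpoint event can only lower the observed rate.

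A smaller matter is the label in SAP 3.2. Section 7.1.1 defines an adverse event whether or not it is related, but unrelated non-serious events are never required from sites. A table presented as all adverse events could be read as more complete than it is.

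**Working it through.** **1. The plan's own figure.** The only step of the sample size that can be checked is the attrition allowance. With 20% attrition (text preceding section 8.4), 224 × 0.80 = 179.2, and 179 / (1 − 0.20) = 223.75, which rounds up to 224. This agrees. Alpha, power and the expected event rate are redacted, so the rest of the calculation cannot be reproduced.

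**2. The reporting rule as a grid** (Protocol 7.3.1, SAP 3.2).

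| Site's view | Related | Unrelated |
|---|---|---|
| Serious | reportable | reportable |
| Non-serious | reportable | no stated duty |

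Only one cell is open. An event is at risk only if the site answers no to both questions.

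**3. Which listed types can fall in that cell.** Several Appendix III definitions contain a seriousness criterion from section 7.1.2: death, heart block needing permanent pacing, pulmonary edema needing hospitalization, and pneumothorax that prolongs the stay or needs a chest tube or surgery. Those are reportable whatever the site thinks of the cause. Others do not force seriousness by definition: a TIA, a deep vein thrombosis (under thromboembolism), a 20% hematocrit fall without transfusion, and an effusion of 1 cm or more without compromise. The first three are the most plausible cases, because a site could point to drug treatment or comorbidity. An effusion or a phrenic nerve paralysis soon after left atrial ablation is hard to call unrelated, so either would normally be reported under the first class.

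**4. Other ways an unreported event could surface.**
- Safety personnel may identify events (10.7.2), but the visible text gives no trigger, and they have little to work from if the site enters nothing.
- The core laboratory reads only TTM, Holter and 12-lead ECG recordings (6.7).
- The healthcare utilization form covers cardiac-related hospital, emergency and urgent-care contacts only (6.6.3).
- A neurological examination is required between 12 and 36 hours after the procedure (6.4). The next scheduled contact is the phone call at 7 ± 2 days (6.6).

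**5. Size per event.** On 224 subjects, 1/224 = 0.45 percentage points. On 179, 1/179 = 0.56. This assumes that the CEC would have upheld the event and, if the rate is counted per subject, that the subject had no other endpoint event.

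**6. Illustration of what a shortfall would do.** Assume an exact one-sided binomial test, passed when the count is at most k, where k is the largest value with Pr(X ≤ k | n, 0.168) ≤ alpha. Let the true rate be 16.8% and let a fraction m of events never reach the CEC, so the observed rate is 0.168 × (1 − m). The chance of a false pass is then:

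| n, assumed alpha | k | m = 0 | m = 5% | m = 10% |
|---|---|---|---|---|
| 179, 0.025 | 20 (11.2%) | 2.4% | 4.5% | 8.2% |
| 224, 0.05 | 28 (12.5%) | 4.7% | 9.0% | 15.8% |

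On 224 subjects the expected count is 0.168 × 224 = 37.6, so 5% and 10% are about 1.9 and 3.8 events. The documents support no particular value of m. The table shows sensitivity, not a forecast.

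**The case against.** A reader might infer that such events never reach the CEC, so that the safety rate is biased. The documents do not support that. Section 10.7.2 gives a second route through safety personnel, and the charter that would hold a trigger list is not available. Section 10.4 requires source records that substantiate adequate adverse event reporting, and section 15.1.3 has sponsor safety staff assessing subjects' safety throughout. What can be shown is the absence of a stated site duty and of a stated trigger.

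The gap is also narrow. All SAEs come in regardless of cause. The relatedness test in section 7.2 is low, asking only for a reasonable possibility that the device contributed, and temporal relationship weighs in it. An early TIA has some protection: same-day discharge is barred, and new neurological findings require a formal consult and imaging (6.4). A deep vein thrombosis may meet the medical-intervention criterion in 7.1.2. All of this stands, and it limits how often the problem can arise.

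A reader might also see a contradiction between sections 3.2 and 7.3.1. There is none in the strict sense: 3.2 says whose adjudication of the collected data counts, not that the committee screens data nobody collected. Nor should the trial be described as unblinded on the strength of the SAP, because section 1.6 is redacted. The point rests on the single-arm design and on the investigator assessing an event after the site's own procedure.

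On the table label, the reportable classes are set out earlier in the same SAP section, so *all* can be read as all reported. That makes it a labelling point only.

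The objection does not supply a rule that sends every listed event type to the CEC. No visible passage does.

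**Conclusion.** The point holds in a limited form. As written, a listed event type that the site judges both non-serious and unrelated need not be reported, and the visible text does not say how else it would reach the committee that is meant to make those two judgments. The number of such events is unknown and may be zero. Each one that the CEC would have upheld lowers the rate by 0.45 points on 224 subjects (0.56 on 179), and any error favours the device. Most listed events are assessed at 7 days, so the figure on 224 is the more relevant one.

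Two stronger conclusions go beyond the documents: that the safety result is biased by some stated amount, or that the conclusion against 16.8% would change. There is no basis for an event count, and the test, alpha and expected rate are redacted. If the charter already contains a trigger list independent of the site's opinion, citing it in the protocol would settle most of the point, provided that sites also have a duty to enter those events. This is a low-cost improvement that makes the bias protection claimed in section 3.2 more secure. It is not a flaw that undermines the design.

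**What to change.** Add a third class to Protocol 7.3.1 and SAP 3.2, for example: *Any event of a type listed in section 4.1.1 or Appendix III, with onset within its endpoint window in section 4.1.1 (7 days after a TactiCath SE procedure, or through 15 months for the three footnoted types), is reported and sent to the CEC regardless of the investigator's assessment of seriousness or relatedness.* Align the CEC charter's trigger list with this sentence and refer to it in section 10.7.2.

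As a minor point, label the SAP 3.2 summary as reported adverse events, meaning SAEs and investigator-attributed AEs.

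The cost is one reporting sentence, one charter line and a table title, plus a few more CEC packets. The observed safety rate may come out slightly less favourable. Treatment, endpoint definition and sample size do not change.

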7.3.2 Serious Adverse Event (SAE) Reporting to Sponsor and IRB/EC

The investigator should report all SAEs to the Sponsor as soon as possible but no later than outlined below.

Clinical Sites	Reporting Timelines
All Sites	SAEs must be reported to the Sponsor no later than 3 calendar days from the day the site personnel became aware of the event or as per the investigative site’s local requirements, if the requirement is more stringent than those outlined.

The date the site staff became aware that the event met the criteria of an SAE must be recorded in the source document. The Investigator will further report the SAE to the local IRB/EC according to the institution's IRB/EC reporting requirements.

An offline form will be made available to allow the investigator to report SAEs in the event the entry cannot be made in the EDC. This does not replace the EDC reporting system. All information must still be entered in the EDC system as soon as feasible.

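### The rule that a post-procedure UTI without a Foley catheter is not an adverse event has no exception for serious cases, and conflicts with the duty to report all SAEs

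*Protocol*

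**What the plan says.** Protocol Section 7.3.1 lists what sites must report. One item is every serious event, whatever its cause: "Serious adverse events, regardless of relatedness to the procedure and/or the ablation catheter will be reported as described in" Section 7.3.2. That section adds "The investigator should report all SAEs to the Sponsor as soon as possible but no later than outlined below", and its table sets 3 calendar days, or less where local rules are stricter.

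Later in Section 7.3.1 comes the UTI rule, in two sentences. The first says that "urinary tract infections (UTIs) that occur after a procedure and do not require a Foley catheter will not be considered adverse events". The second says that "UTIs that require a Foley catheter will be reported as AEs if related to the procedure or meet serious criteria". SAP Section 3.2 carries the same two sentences alongside the same requirement to report serious events regardless of relatedness.

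The definitions are in Section 7.1. An AE is broad: "An adverse event (AE) is any untoward medical occurrence, unintended disease or injury, or untoward clinical signs". Seriousness is then a property of an AE: "If the AE meets any of the criteria below, it is regarded as a serious adverse event (SAE". Among the criteria, under serious deterioration in health, is "in-patient hospitalization or prolongation of existing hospitalization".

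**The concern.** The first UTI sentence does not set a reporting threshold. It takes the event out of the AE category altogether, and the mention of serious criteria comes only afterwards, for UTIs that need a Foley. Take a UTI treated without a Foley that leads to admission or a longer stay. Under the general definitions it is an SAE. Under the UTI rule it is not an AE, and so cannot be an SAE.

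What is at stake is completeness and consistency of safety reporting: the 3-day report to the sponsor, onward reporting to the IRB or ethics committee, and the AE, SAE and (for related events) SADE summaries in SAP Section 3.2. With up to 25 sites, different readings could mean that like events are counted at one site and not at another. Any omission can only lower the counts.

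**Working it through.** The plan states no figure on this point, so the check is a comparison of the passages.

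**Following the UTI rule literally**

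1. Protocol 7.1.1: a UTI is an untoward medical occurrence, so by default it is an AE.
2. Protocol 7.3.1 and SAP 3.2, first UTI sentence: after a procedure and without need of a Foley, it is not an AE. The sentence has no seriousness condition and no time limit.
3. Protocol 7.1.2: an SAE is an AE that meets a criterion. No AE, therefore no SAE.
4. Protocol 7.2.1 and 7.2.2: an adverse device effect is a related AE, and a SADE is a serious one. No AE, therefore no SADE either.
5. Protocol 7.3.1 and 7.3.2: the duty to report SAEs is then never triggered.

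**Following the general rules instead**

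The same event is an AE by 7.1.1. If the hospital stay reflects serious deterioration, it is an SAE by 7.1.2. It is then reportable by 7.3.1 whatever its cause, and within 3 calendar days by 7.3.2.

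**Side by side**

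| Post-procedure UTI | UTI rule | General rules (7.1.1, 7.1.2, 7.3.1, 7.3.2) |
|---|---|---|
| Foley needed, serious | Reported | Reported |
| No Foley, serious | Not an AE | Reported as an SAE |
| No Foley, not serious | Not an AE | An AE, reported only if related |

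The middle row is the conflict: two equally serious UTIs are treated differently on Foley use alone.

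**Is the exception supplied elsewhere?** No passage restores serious UTIs without a Foley. Two features of Section 7.3.1 make it hard to read one in. The seriousness clause was written for the other kind of UTI. And the neighbouring exclusion, for recurrence of AF, AFL or AT, carries its own exception for recurrences significantly worse than baseline. Nor does it help to suppose that UTIs without a Foley were thought unrelated to the procedure, because SAEs are reportable regardless of relatedness.

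**Size.** The documents give no UTI rate. As an assumption only, let 1% to 3% of the 224 subjects have a post-procedure UTI, and let 10% to 30% of those be serious and treated without a Foley:

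- Low: 224 × 0.01 × 0.10 = 0.22 events
- High: 224 × 0.03 × 0.30 = 2.02 events

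The range of about 0.2 to 2 rests wholly on the assumed rates and includes effectively no events.

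**Primary endpoint.** UTI is not among the components listed in Protocol 4.1.1 and SAP 1.4.1, so the primary safety rate and its test are unaffected.

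**The case against.** The strongest case against is that nothing need go wrong in practice. The protocol's compliance statement says the most stringent requirement must always be followed, which points towards reporting. Section 7.3.2 speaks of all SAEs. Under Section 10.7.2 the Clinical Events Committee also considers events found by safety personnel, and Section 15.1.3 has internal safety staff assessing continuing safety. This has some weight: a careful site may well report. But the compliance statement is general and does not rank one section of the protocol over another, and the other backstops work only if the event comes to someone's notice.

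A reader might infer that a hospitalised urosepsis is certain to escape SAE reporting. The documents do not support that. The UTI sentence names urinary tract infections and says nothing of sepsis. Sepsis is an untoward occurrence in its own right under 7.1.1, and a site could report it as a separate event. The gap is narrower: an event recorded purely as a UTI.

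A reader might also infer that the reported safety profile will be too favourable. The direction is right if events are omitted, but no figure in the documents shows that any will be, and loss from the SADE summary further requires a relation to the device or procedure. Nor does the entry for infections among the anticipated device effects in Section 15.1.1 add a contradiction: it is generic, does not name UTI and sets no reporting rule.

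**Conclusion.** The point stands as a contradiction in the safety-reporting text. Read literally, Protocol 7.3.1 and SAP 3.2 exclude a serious UTI treated without a Foley catheter, while the AE and SAE definitions and the SAE reporting rules would include it. Which rule governs is left open, so the finding is that sites are given two incompatible instructions, not that SAEs will certainly be lost.

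The consequences are limited to SAE reporting and the descriptive summaries. No hypothesis test, performance goal or sample size depends on it. The number of events is likely to be very small, though that is a judgement on assumed rates. It is still worth correcting, because SAE reporting is mandatory and the repair is trivial.

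**What to change.** In the first UTI sentence of Protocol 7.3.1, add the clause *unless they meet the serious criteria of Section 7.1.2*. Make the same addition in SAP 3.2, pointing to Section 7.1.2 of the protocol. The UTI rule then agrees with the SAE definition and the reporting duty, and the outcome of a serious UTI no longer turns on Foley use. Non-serious UTIs without a Foley remain excluded, as now.

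The cost is one clause in each document, with the usual amendment handling and a note to sites, and at most a few extra SAE forms. No endpoint, analysis or treatment changes.
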